8.3.2. Analysis Data Sets

The primary inference for efficacy in the study will be made from the analysis of subjects randomized in Part B of the trial. The primary efficacy dataset will comprise all adjudicated events occurring post randomization up to and including Week 12 [Day 84] (including events collected after discontinuation of IP).

8.3.3. Treatment Comparisons

8.3.3.1. Primary Comparisons of Interest

The primary comparison of interest is the comparison of the survival functions of adjudicated MACE followed by CV death or MI in a closed testing procedure for losmapimod vs. placebo (using a stratified log-rank test) in Part B. The ITT population will be utilized for this comparison. The comparison will be performed for events occurring within the period from randomization to Week 12 at the two-sided 5% significance level.

8.3.3.2. Other Comparisons of Interest

Leading Cohort (Part A)

The primary efficacy comparison for the leading cohort will be the comparison of the incidence and hazard rates of adjudicated and pending MACE events for losmapimod vs. placebo occurring to Week 12 during Part A of the study.

Secondary Endpoints

The relative effects of losmapimod vs. placebo will also be compared across a number of secondary endpoints.

Secondary efficacy outcomes are defined in Section [6.3.2](#)

The primary and each of the secondary endpoints will be analysed through 4, 12, and 24 weeks unless otherwise stated.

Due to the reduced number of events for the secondary outcomes the analyses may have less power in which case they would be less likely to achieve statistical significance. Details of additional multiplicity considerations are provided in the RAP.

Combined Analysis of Parts A and B

A supportive analysis of efficacy will be performed for the primary and secondary endpoints combining data from Part A and Part B. Further details are provided in Section 8.3.5.1.

8.3.4. Interim Analysis

An IDMC will review data from both stages periodically throughout the trial and may recommend stopping the trial for safety at any time.

There are no plans to stop either part of the study early for benefit and in particular this will expressly not occur during review of Part A. Should, in the course of reviewing mortality data for safety, the IDMC consider a recommendation to stop Part B early for a highly significant difference in mortality (e.g., $p < 0.001$) favoring losmapimod (i.e., efficacy) then both the primary endpoint and the principal secondary endpoint would be examined at that time and compelling evidence of benefit for both the primary endpoint and the principal secondary endpoint would be required e.g., $p < 0.001$ (using a Haybittle-Peto like approach). This approach would essentially preserve the alpha level at 5% in the final analysis and therefore there are no plans to adjust the alpha level in the final analysis. The timing and number of planned evaluations of safety, as well as assessments for futility, by the IDMC will be specified in the separate IDMC Charter.

The analysis of Part A is not considered to be an interim analysis as the primary inference for the study will be determined only from the subjects in Part B of the trial.

8.3.5. Key Elements of Analysis Plan

Any deviations from the original analysis planned in the protocol agreed upon prior to finalization of the RAP, will be described in that document. Any additional changes to the planned analysis will be described in the final clinical study report.

8.3.5.1. Efficacy Analyses

The primary analysis will be based on a stratified log-rank test with a stratified Cox-regression model used to estimate the hazard-ratio and its 95% confidence interval (both analyses stratified by NSTEMI/STEMI). Key secondary endpoints will be assessed using the same methods as the primary endpoint, with overall significance controlled for multiplicity at the 5% level. Cumulative event rates will be calculated using the Kaplan-Meier method through to 12 weeks.

Treatment comparisons will be presented as forest plots of the hazard ratios and 95% confidence intervals and the effect over time illustrated with Kaplan-Meier plots. Analyses that combine data from Parts A and B will further stratify on which part of the

study subjects were enrolled, in addition to NSTEMI/STEMI status. The validity of the proportional hazards assumption will be assessed (details will be provided in the RAP).

Center-based randomization is planned for operational efficiency in managing drug supply, with a centrally administered randomization code consisting of permuted blocks stratified according to centre. However, as the use of center is purely for operational purposes it is not planned to include centre as a stratification parameter in the statistical analyses.

Sensitivity Analyses

Sensitivity analyses of the primary efficacy endpoint will be performed to assess the robustness of the primary inferences made from the main cohort (Part B).

- An analysis of on-treatment adjudicated MACE (including up to 3 days post discontinuation of IP \approx 5 half-lives) will be performed in the ITT population.

Analyses of efficacy will be performed for pre-specified subgroups to support the proposed indication. Subgroups and covariates of specific clinical interest include (but are not limited to) type of ACS event (NSTEMI or STEMI), intent for early invasive vs. conservative management, gender, diabetes status, age, time from symptom onset to treatment, and baseline hsCRP levels. Further details will be defined in the RAP.

Multiplicity

Issues related to multiplicity arising from testing the primary endpoint and the principal secondary endpoint and other key endpoints (defined in Section 6.3.2) will be addressed using a serial gate keeping procedure. Further details relating to multiplicity will be addressed in the RAP.

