***NSTEMI** that is presumed spontaneous (Universal Definition Type 1) and is defined as ischemic chest discomfort (or equivalent) that occurs or persists at rest with at least 1 episode lasting ≥ 10 minutes and is accompanied by a diagnostic elevation in cardiac troponin above the upper limit of normal (99th percentile decision-limit) according to the local laboratory without persistent ST segment elevation. If cardiac troponin is not available, then creatine-kinase MB isoenzyme (CK-MB) must be above the upper limit of normal. The biomarker should exhibit a rising and/or falling pattern when serial testing is available prior to randomization.*

***STEMI** is defined as ischemic chest discomfort (or equivalent) that occurs or persists at rest with ST segment elevation of at least 0.1 mV in 2 or more contiguous leads or new (or presumed new) left bundle branch block (LBBB) and a presumed diagnosis of STEMI.*

NOTE: *Subjects with clinical or laboratory manifestations of ACS (e.g., ST-elevation or increase in cardiac enzymes) that are believed to be secondary to other apparent illness (e.g., sepsis, profound anemia, hypertensive emergency or decompensated heart failure, coronary embolism or dissection; Universal Type 2 MI) or known to be procedurally related (Type 4 - including stent thrombosis- or Type 5) are **not** considered to meet these criteria for NSTEMI or STEMI.*

4. With the following timing of symptoms:

NSTEMI: Presence of ischemic symptoms (≥ 5 minutes) at rest within 24 hours prior to randomization (may include qualifying episode).

STEMI: Onset of qualifying ischemic symptoms within 12 hours of randomization.

5. All subjects must also have at least one of the following additional predictors of cardiovascular risk:

- a. Age ≥ 60 years at randomization.
- b. History of documented MI (known or presumed Type 1 MI) prior to qualifying ACS event.
- c. History of CABG prior to qualifying ACS event.
- d. NSTEMI with new ischemic ST-segment depression ≥ 0.1 mV in ≥ 2 contiguous leads.
- e. Diabetes mellitus requiring pharmacotherapy.
- f. Coexistent clinically diagnosed arterial disease in at least 1 peripheral arterial territory, defined as:
 - History of non-cardioembolic (known or presumed), ischemic stroke (confirmed by medical records or history) or

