8.1. Hypotheses

The primary efficacy analysis (Part B) will assess the time to first occurrence (in days) of MACE from randomization up to and including Week 12 (Day 84).

The primary objective of the study is to assess superiority of treatment with losmapimod relative to placebo on top of a background of standard care.

The primary analysis will assess superiority of treatment with losmapimod relative to placebo on time to first occurrence of MACE through 12 weeks of therapy. Statistical significance will be assessed at the two-sided 5% level by a log-rank test, stratified by NSTEMI/STEMI status at baseline.

A two-sided 5% significance level will be used to test the following hypotheses:

- Null hypothesis: The hazard functions for MACE are the same for both losmapimod and placebo treated subjects
- Alternative hypothesis: The hazard functions differ between losmapimod and placebo treated subjects

A stratified Cox-regression model, stratified by NSTEMI/STEMI, will be used to estimate the hazard-ratio and its 95% confidence interval. A hazard ratio < 1 will correspond to a benefit of losmapimod relative to placebo.

The primary efficacy endpoint (MACE) will be tested first and if the null hypothesis is rejected, the principal secondary endpoint (CV death or MI) will be tested, before proceeding to other secondary endpoints as part of a serial gate keeping procedure, the details of which are addressed in the RAP. If either the primary or principal secondary null hypotheses fail to be rejected, the other secondary endpoints will be tested in an exploratory manner.

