8.2.1. Sample Size Assumptions

Assessment of MACE Efficacy from Part A

The pivotal and powered assessment of efficacy will be provided by Part B of the study, with Part A providing an exploratory assessment to support continuation to Part B.

Whilst an exploratory cohort could not be well powered for formal assessment of efficacy, the precision with which the MACE effect size can be estimated from Part A has been considered. For example, with approximately 200 subjects anticipated to experience at least one MACE event, an observed relative risk of 0.8 would have an associated 95% confidence interval of approximately 0.61 to 1.05, whilst an observed relative risk of 1.0 would have a 95% confidence interval of approximately 0.76 to 1.31. Given the limitations on precision that would be expected in an exploratory context, the decision to progress to Part B will be multifaceted.

Assessment of Efficacy in Part B

The size of Part B has been determined based on an event target of 1,400 adjudicated primary endpoint events. It is anticipated that approximately 22,000 subjects will be

recruited to achieve this event target. The primary endpoint event target is expected to include 1,000–1,200 CV death or MI events. These estimates are based on a projected 12 week MACE event rate of ~7% for the placebo group, and an assumed 20% relative risk reduction for subjects in the losmapimod group. Within the composite of MACE, it is estimated that the incidence of CV death/MI will be 5% to 6% and that SRI-UR will be 1% to 2%.

The principal efficacy evaluation will occur up to Week 12 with additional evaluations of efficacy at Weeks 4 and Week 24.

A total of 1,400 adjudicated primary MACE events (CV death, MI, and SRI-UR) occurring within the principal study time point of 12 weeks will provide approximately 90% power to detect a 16% reduction in risk (hazard ratio=0.84) at a 5% significance level. At the 5% significance level, the minimum detectable effect (i.e., the smallest effect to give a significant p-value) is approximately 10%.

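### Optional efficiency gain, low priority: the primary test adjusts only for NSTEMI/STEMI, and prespecified adjustment for baseline predictors already collected would add a little information at almost no cost

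*Protocol*

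**What the plan says.** The protocol fixes the primary test itself and does not leave it to the analysis plan. Section 8.1 states: "Statistical significance will be assessed at the two-sided 5% level by a log-rank test, stratified by NSTEMI/STEMI status at baseline". Section 8.3.5.1 repeats the method: "The primary analysis will be based on a stratified log-rank test with a stratified Cox-regression model used to estimate the hazard-ratio", adding "both analyses stratified by NSTEMI/STEMI", and the opening summary of section 8 agrees. Centre is used in the randomization, but "it is not planned to include centre as a stratification parameter in the statistical analyses".

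Inclusion criterion 5 in section 4.2 reads: "All subjects must also have at least one of the following additional predictors of cardiovascular risk". It then lists age, prior MI, prior CABG, ST depression in NSTEMI, treated diabetes and arterial disease outside the heart. Section 6.1 has cardiovascular history and risk factors assessed at baseline. Table 1 schedules a central chemistry sample at randomization, and section 6.4.15 includes creatinine and eGFR in that panel. None of these enters the primary test or model. Section 8.3.5.1 does name age, gender, diabetes, hsCRP and others as subgroups and covariates of interest, with details left to the analysis plan.

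On size, section 8.2.1 says that "A total of 1,400 adjudicated primary MACE events (CV death, MI, and SRI-UR) occurring within the principal study time point of 12 weeks" will give "approximately 90% power to detect a 16% reduction in risk (hazard ratio=0.84) at a 5% significance level".

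**The concern.** When outcome risk varies between subjects, a log-rank test that ignores the predictors of that risk leaves some information unused. In a Cox model the loss shows as a hazard ratio pulled slightly toward 1 with no matching fall in its standard error.

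Here the data would be in hand, and the protocol itself calls the criterion 5 factors predictors of cardiovascular risk. By the protocol's own rates, the one factor used carries almost no prognostic information.

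The power has little reserve at hazard ratio 0.84. Section 8.2.1 also lets recruitment close before 1,400 events if Part B is expected to exceed 24,000 subjects, and Table 4 reaches that point at a placebo rate of 6.4% (24,200 subjects). Once the cap binds, the analysis is one of the few places left to gain precision.

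**Working it through.** **Inputs from the protocol.** 1,400 events, about 22,000 Part B subjects, 1:1 allocation, two-sided 5%, hazard ratio 0.84, stated power about 90% (sections 3.1, 8.1, 8.2.1). NSTEMI and STEMI rates of 7.1% and 6.0% (section 8.2.1). **Assumed:** the prognostic strength of the other predictors.

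**1. The protocol's own figure.** Schoenfeld: power = Φ(√(1,400/4) × |ln 0.84| − 1.96) = Φ(18.71 × 0.1744 − 1.96) = Φ(1.302) = 90.4%. Events needed for 90% power are 1,383 (Schoenfeld) or 1,390 (Freedman). The stated figure reproduces.

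**2. What the NSTEMI/STEMI stratum contributes.** The share of log-rank information lost by omitting a predictor is approximately p × θ. Here p is the event proportion and θ is the squared coefficient of variation of subject risk.
- p = 1,400/22,000 = 0.0636.
- With an equal mix (assumed), mean risk is 6.55% and half the difference is 0.55 points, so θ = (0.55/6.55)² = 0.00705.
- p × θ = 0.00045, or about 0.04%.

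**3. What other predictors could contribute.** Simulation of 22,000 subjects with about 1,400 events, hazard ratio 0.84 and a normal risk score on the log-hazard scale, 2,500 replicates per row. Gain = (mean z adjusted / mean z unadjusted)² − 1, using Cox models with and without the score. For this score θ = exp(SD²) − 1.

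| SD of log-risk | c-statistic | Simulated gain | p × θ |
|---|---|---|---|
| 0.30 | 0.59 | 0.5% | 0.6% |
| 0.50 | 0.65 | 1.8% | 1.8% |
| 0.70 | 0.69 | 4.1% | 4.0% |
| 0.85 | 0.73 | 6.6% | 6.7% |
| 1.00 | 0.76 | 9.6% | 10.9% |

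A separate simulation at 7% placebo risk gave 0.8%, 2.0%, 4.6% and 7.9% for SD 0.3, 0.5, 0.7 and 0.9. A c-statistic of 0.65 to 0.75 therefore corresponds to a gain of about 2% to 8%.

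**4. In events and power at hazard ratio 0.84.**
- 2%: 1,400 × 1.02 = 1,428 events (+28), power 90.9%.
- 4%: 1,400 × 1.04 = 1,456 events (+56), power 91.4%.
- 8%: 1,400 × 1.08 = 1,512 events (+112), power 92.4%.

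**5. If the cap binds.** At a 6.0% placebo rate, with Table 4's hazard ratio of 0.8 used for counting events, 24,000 subjects give 12,000 × 0.06 × 1.8 = 1,296 events. Power at 0.84 is Φ(18 × 0.1744 − 1.96) = 88.1%. The gain scales with the event proportion: 1,296/24,000 = 0.054, and 0.054/0.0636 = 0.85, so 2% to 8% becomes about 1.7% to 6.8%. That is 1,318 to 1,384 effective events and power of about 88.6% to 90.0%.

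**The case against.** The strongest reply is that nothing is wrong. The test is stated consistently, it stratifies on the ACS type used in the randomization (section 5.2), and its power is correct. A reader might infer from the unused predictors that the trial is underpowered or its hazard ratio invalid. The protocol supports neither: step 1 reproduces the power, and the planned test is valid without covariates. At the 20% reduction behind the subject number, 1,400 events give 98.7% power, and a 2% to 8% gain lifts that only to between 98.8% and 99.1%. This objection stands and sets the priority low.

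A reader might also take 2% to 8% as a known loss. It is not, because it rests on an assumed c-statistic. Every subject must already carry a risk predictor, which may narrow the spread of risk. The simulations used one complete, correctly specified score in a Cox model, which is a favourable case for mostly binary covariates with some values missing. The adjusted log-rank test was not itself simulated. The p × θ approximation suggests a gain of the same order, and somewhat less if the covariates track risk imperfectly.

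Nor does criterion 5 establish all six factors for every subject. It asks for at least one, so a subject aged 60 or over qualifies on age alone. Current peripheral arterial disease needs an ankle-brachial index, which Table 1 does not schedule, and the ST-depression item is defined only for NSTEMI. These points shorten the covariate list but leave age, history, treated diabetes and eGFR.

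Finally, the unseen analysis plan may contain a supportive adjusted analysis, so its absence here is no fault. The point concerns the primary test, which the protocol does fix.

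**Conclusion.** This is a free-to-cheap improvement of low priority, not a correction of an error. The primary test and Cox model use only NSTEMI/STEMI, a factor worth about 0.04% of the information on the protocol's rates and an equal mix. Predictors collected anyway could recover about 2% to 8% if their joint c-statistic is about 0.65 to 0.75. That equals 28 to 112 events and moves power at hazard ratio 0.84 from 90.4% to about 90.9% to 92.4%. With weak predictors (c about 0.6) the gain is under 1%. The direction is secure; the size depends on a prognostic strength that the protocol does not give.

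**What to change.** Before Part B is unblinded, amend sections 8.1 and 8.3.5.1, and the summary at the start of section 8, as follows.

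- **Primary test:** a covariate-adjusted log-rank test stratified by NSTEMI/STEMI.
- **Covariates, fixed in advance:** age (continuous), prior MI, prior CABG, treated diabetes and baseline eGFR. If ST depression is used, use it only within the NSTEMI stratum. Leave out peripheral arterial disease defined by ankle-brachial index.
- **Missing baseline values:** one simple rule that does not depend on treatment, such as a missing-value indicator or the median.
- **Supportive results:** the unadjusted stratified log-rank test and stratified hazard ratio, reported as now planned.

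Pooled Part A data lie outside the primary efficacy analysis and could give a c-statistic to replace the assumption.

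Cost: protocol and analysis-plan wording, with no new data, visits or subjects. Downsides: the covariates must be fixed in advance. The method carries over to the key secondary endpoints, which follow the primary method. Any adjusted Cox hazard ratio is conditional on the covariates and should be labelled so.

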8.3.5.2. Safety Analyses

The total AE experience (non-serious combined with serious AEs) will be reported based on the on-treatment period in accordance with the time-and-events schedule (Table 1). SAEs and AEs of special interest occurring after discontinuation of IP will also be reported. Full details of all safety data reporting (including laboratory data) will be described in the Analysis Plan.

The primary population for all safety assessments will be the Safety Population, defined as all randomized subjects who have received at least one dose of IP. Subjects will be analysed according to the treatment which they actually received. Clinical interpretation will be based upon review and displays of AEs, laboratory values and vital signs. All AE data will be coded using MedDRA and all medication terms will be coded using GSKDrug. Additionally, safety data will be summarized for the leading cohort (Part A) prior to the initiation of the main phase of the study (Part B).

Additional details regarding planned statistical analyses for safety data will be provided in the RAP.

8.3.5.3. Health Outcomes Analyses

Health economic outcomes will be assessed in this study including medical resource utilization and health status assessment, which will both be used to assess the cost-effectiveness of losmapimod in the ACS population. With the exception of EQ-5D-5L, the events of interest will be measured at discharge, Week 4, Week 12, and Week 24 (end of study) with possibility for an extension registry. The EQ-5D-5L will be collected in a select number of countries in Part B1 at discharge, Week 12, and Week 24 (end of study), while it will be collected in those same countries in Part B2 at discharge and Week 12 only. The paper questionnaire will be completed by the subject at the designated clinic visits and it will not be completed at the Week 24 phone visit in Part B2.

The health economic evaluations, to be detailed in a separate Economic Statistical Analysis Plan, will include: total treatment costs; cost per vascular event avoided; cost per life years saved (LYS); and cost per quality-adjusted life years (QALY) gained.

8.3.5.4. Biomarker Analyses

Details regarding planned statistical analyses for biomarker data will be provided in a separate RAP.

8.3.5.5. Pharmacokinetic and Pharmacokinetic/Pharmacodynamic Analyses

The objective of the pharmacokinetic analyses is to further develop the population PK model previously developed in Phase 2 in order to predict individual losmapimod exposures. The population PK model will be parameterized for oral clearance (CL/F), apparent volumes of distribution of the central compartment (V₂/F) and other parameters specific to the model. The potential effects of subject demographics (e.g., age, sex, weight, concomitant medications, and concurrent diseases) will be examined for their effect on clearance and volume.

The plasma concentration data will be analyzed with the use of the nonlinear mixed effects modeling program NONMEM (version 7.2 or higher). The prior PK model developed from data collected in the SOLSTICE trial will be used as prior information for this analysis. The initial estimation method to be used will be the iterative two-stage (METHOD=ITS) followed by METHOD=BAYES. The objective function will be obtained by importance sampling using the EONLY=1 option.

During each step in the model building process, improvements to the model will be assessed by evaluation of the agreement between the observed and predicted plasma concentrations, reductions in the range of weighted residuals, uniformity of the distribution of the conditional weighted residuals versus the predicted concentrations about the line of identity, and increases in the precision of the parameter estimates, as well as reduction of the terms for inter-individual variability and random residual variability. Assessment of the log likelihood ratio test will also be conducted as a means of assessing improvement in the model.

Once a final pharmacokinetic model has been developed, individual steady-state AUC(0- τ) values will be generated from the individual Bayes estimates of clearance. These

exposure values will be used along with adverse event data in a logistic regression analysis in order to determine if a relationship exists between losmapimod exposure and adverse events.

Pharmacokinetic analysis will be the responsibility of the Clinical Pharmacokinetics Modeling and Simulation Department, GlaxoSmithKline. All PK data will be stored in the Archives, GlaxoSmithKline Pharmaceuticals, R&D.

Details regarding the planned statistical analyses of the PK/PD data will be provided in a separate Data Analysis Plan (DAP)

